Exclusion criteria: Individuals will be excluded due to: 1) severe concurrent illness or pain, including unhealed decubiti, severe neuropathic or chronic pain syndrome, infection (e.g. bladder), hypertension, cardiovascular disease, pulmonary disease, severe osteoporosis (history of fractures), active heterotopic ossification in the lower extremities, or history of peripheral nerve injury in the legs; 2) < 24 on Mini-Mental Exam²²; 3) severe autonomic dysreflexia; 4) history of cardiovascular/pulmonary complications; 5) pregnancy because of unknown effects of AIH on a fetus, although women of childbearing potential will not otherwise be excluded; 6) undergoing concurrent physical therapy; 7) history of diabetes. Caffeine can potentially alter sugar metabolism and, thus, persons diagnosed with diabetes will be excluded from participating in the caffeine portion of this study; 8) history of cirrhosis. Cirrhosis is known to increase the elimination time of caffeine and, thus, persons diagnosed with cirrhosis will be excluded from participating in the caffeine portion of this study; and 9) history of caffeine allergies or intolerances. Participants with a history of caffeine allergies or intolerances will be excluded from participating in the caffeine study.

Inclusion of women and minorities: We will recruit persons with SCI to include women and minorities. To protect against possible unknown side effects of dAIH, women who are pregnant

DETAILED STUDY PROTOCOL

may not take part in this study as the effects of dAIH on the developing fetus have not been studied. If a woman is of childbearing ability, birth control will be recommended for use throughout the study.

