Our study coordinator, study physicians, physical therapists, PI ([name]), and research collaborators recruited subjects using a variety of strategies shown effective in the past. First, the team identified potential subjects using Institutional Review Board (IRB) approved resources to inform persons with SCI that are currently admitted to inpatient rehabilitation/outpatient units of Spaulding Rehabilitation Hospital, Boston University Medical Center, Massachusetts General Hospital, Gaylord hospital, Albany Medical Center, and Maine Medical Center. Subjects also will be recruited by word of mouth and flyers at these facilities. Eligible subjects screened at INSPIRE Laboratory, Spaulding Rehabilitation Hospital Cambridge, MA. At the screening visit, subjects informed of this project, their potential involvement, the possible benefits, and risks, and their right to terminate participation at any time without penalty. Qualifying subjects in agreement with the study details asked to sign the informed consent and HIPAA form approved by Partners IRB. All potential subjects entered the study according to the inclusion/exclusion criteria above and following medical clearance. Experiments will be conducted at the Spaulding Rehabilitation Hospitals.

11. Interventions

- a. Intervention Procedures: This placebo-controlled study will examine the combined effects of caffeine (vs. placebo) and AIH (vs. SHAM) on walking performance in persons with chronic, iSCI. Participants will receive three combinatorial interventions in random order: placebo+AIH, caffeine+AIH, caffeine+SHAM. The order of interventions will be block randomized. The initial screening and evaluation procedures are similar for all participants. For each intervention, participants will complete up to 8 visits/intervention (1 baseline/intervention + 5 treatment days/intervention + 2 follow-up days/intervention). Participants will complete a total of 24 visits (8 visits/intervention x 3 interventions) after the initial screen. Participant enrollment and allocation will be completed during the screening visit. Baseline will be recorded up to 3 days prior to the first intervention.

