Caffeine intervention (caffeine or placebo): Before each intervention round, subjects will be asked to avoid caffeine-containing substances for 48 hrs. (half-life ~7 hrs.)^{21,23} prior to arrival to control for baseline plasma levels of caffeine.²⁰ Subjects will then ingest capsules containing either placebo (sucrose) or caffeine (up to 400 mg). USP and FCC grade caffeine and placebo capsules will be sourced to a private independent compounding pharmacy (Johnson Compounding Pharmacy, Waltham MA, USA). The study PI ([name]) will hold a Class VI Drug License and the study physician ([name]) will write the prescription for caffeine or placebo and have the prescription sent to the compounding pharmacy. The compounding pharmacy will then dispense the caffeine or placebo to the subject for use in the study. Administration will also be overseen by a physician member of the study team.

Persons experiencing caffeine-induced adverse side effects (e.g., dizziness) will be excluded. Since caffeine is a diuretic, we will encourage subjects to empty bladders prior to AIH (or SHAM). To monitor caffeine levels and identify subject-to-subject differences in absorption, blood samples will be collected before capsule consumption and post-AIH or SHAM intervention on days 1 and 5.^{17, 24, 25}

DETAILED STUDY PROTOCOL

Safety considerations for caffeine: Caffeine is commonly used on a daily basis, with an average adult consumption of up to ~6 mg of caffeine per kg of body weight and heavy consumers consuming ≥ 9 mg/kg,^{19, 26} including in persons with SCI.²⁷ High doses of > 6 mg/kg caffeine have been tested in humans for athletic performance enhancement without reported adverse effects.^{20, 28, 29} In persons with SCI, 6 mg/kg has been shown enhance athletic performance without reported adverse effects^{20, 27} and no significant or unsafe changes in blood pressure, heart rate, or respiration were seen.²⁷ Thus, up to 6 mg/kg is within a reasonable and safe range, and that caffeine was safe and well-tolerated by persons with SCI.

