- b. Criteria for discontinuing or modifying allocated interventions: The interventions will be stopped, and immediate care provided if any significant adverse effects, such as rapid heart rate, dizziness, nausea, or a significant change in blood pressure, are detected or self-reported by the study participant. Participants with diabetes, cirrhosis, a history of autonomic dysreflexia, caffeine allergies or sensitivities, or females who are pregnant will be excluded from this portion of the study. Due to the diuretic effects of caffeine, subjects will be asked to empty their bladders prior to consumption. Throughout the 30 min wait time and experimentation, blood pressure and heart rate will be monitored. Any adverse effects will be reported and assessed. Our study team will be prepared to discontinue treatment and offer immediate care if any significant adverse effects, such as rapid heart rate, systemic hypertensive event, dizziness, or nausea are detected or self-reported by the subject. We will define a systemic hypertensive event as a systolic pressure exceeding 140 mmHg and/or diastolic pressure exceeding 90 mmHg.^{46,47}
- c. Strategies to improve adherence to intervention protocols: To improve adherence to intervention protocols, participants will complete these protocols within the INSPIRE Laboratory. We will provide participants with a stipend and reimburse them for travel and lodging costs.
- d. Relevant concomitant care and interventions permitted or prohibited during the trial: Patient Monitoring Equipment. Patient Monitor Systems will be used to monitor hemodynamic changes during and following intermittent hypoxia [Smith Medical Systems, USA; Nonin, USA; Welsh-Allyn, USA; Biopac Systems Inc, USA and Masimo; Irvine, CA, USA]. These devices provide estimates of blood pressure, heart rate, oxygen saturation, and pulse rate variability. These measures will be monitored continuously during breathing protocols to ensure subject safety. The blood pressure cuff transducer will be secured around the upper arm during pressure measurements.

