- Concealment mechanism – We will conceal the intervention allocation from the evaluators performing the assessments, treatment administrators, and the study participant.
- Implementation – The PI and biostatistician will generate the allocation sequences for the cross-over study. The trial coordinator will enroll participants and study staff who are not training or assessing the participants will assign the block randomized interventions.

11. Sample size

Twenty individuals with chronic (> 6 months post injury), motor-incomplete SCI (i.e., American Spinal Injury Association Impairment Scale (AIS) C or D) will be recruited for the study. Prior to the start of this clinical trial, we estimated the number of participants needed to achieve study objectives. In particular, our sample size computation focused on treatments: caffeine+dAIH versus placebo+dAIH alone. Our preliminary study on the effects of caffeine prior to single AIH sequence (vs placebo+SHAM) on 10MWT showed a decrease of 2.4s±1.2s. Under the hypothesis of an additive effect of caffeine+dAIH (vs. placebo+dAIH), we anticipate the difference in walking speed (10MWT time) change between treatments would be approximately 0.06m/s. With N=20 cross-over participants (includes 17% attrition rate), a repeated measures ANOVA comparing 4 treatments across 4 time points, using pooled SD of 1.3s across days, will be sensitive to detect a difference at power of $1 - \beta = 0.80$ ($f=0.7$, $F_{3,12}=3.5$; $p=0.4$, $\alpha=.05$).

12. Framework

This placebo-controlled study will examine the combined effects of caffeine and AIH results in greater walking performance than either intervention alone. However, this trial will not evaluate the potential superiority or equivalence of caffeine+AIH to standard of care treatments for persons with chronic iSCI.

13. Statistical interim analyses and stopping guidance

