[name] will fulfill the responsibilities identified in the study's delegation log. These responsibilities include collecting and tracking data forms and instituting quality control measures for data entry verification and study compliance. She will request further documentation such as physician and/or procedure notes in the event of observed or reported adverse events or deviations. They also will be responsible for auditing the database and confirming the overall integrity of the data. The PI ([name]) will ensure that all information pertaining to significant new developments and unanticipated adverse events are provided to the appropriate regulatory authorities, the Investigators, and to the IRB. Quality control measures for this study will be conducted at regular intervals ensure the highest standard of clinical research conduct. These inspections are conducted in order to verify adherence to the protocol and the completeness and accuracy of the data.

20. Analysis populations

In this cross-over trial, participants will receive the primary intervention (caffeine+AIH) as well as the control conditions (placebo+AIH, caffeine+SHAM). We will perform safety-related assessments on each study participant. We anticipate all participants will participate in the 3 interventions as prescribed, will attend all test visits, and will not have any serious protocol violations.

V. Trial Population

21. Screening data

There will be no statistical testing completed for clinical characteristics. We will summarize the sex, duration of SCI, level and severity of SCI, age, weight, as well as biomarker measures (see Table below). The categorical data will be presented using counts and percentages. The continuous variables (e.g., outcome measures) will be presented using the mean, median, standard deviation (SD), minimum, maximum, and number of participants with an observation (n).

22. Eligibility

Potential subjects will be informed about the objectives of the study and must meet all inclusion and exclusion criteria (see Appendix 1 for sample Informed Consent Form). They will be required to read and sign approved consent and HIPAA forms prior to participation to allow access to medical information from their physicians.

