Alternative statistical methods: If distributions are not normal, we will perform comparable nonparametric tests. If baseline measures are significantly different between sessions (interventions), an analysis of co-variance (ANCOVA) will be used to analyze the data.

Blinding integrity analysis: we plan to rigorously quantify blinding integrity here. We will ask participants and raters to guess the intervention received at the end of each intervention and indicate guess confidence using a Likert scale.^{38,39} We will use a contingency table and Fischer's Exact Test to determine if the probability of correct guessing is different from chance. Using multivariate logistic regressions, we also will assess factors that may influence guessing (i.e., adverse events, perceived effects, and sensorimotor changes). In the event of a medical emergency, we will unblind the PI, study participants, and care provider. We also will notify IRB of treatment allocation during adverse event reporting as necessary.

CYP1A2 analysis: we will perform subgroup analysis on our study cohort to determine the extent to which differences in caffeine metabolism due to CYP1A2 polymorphisms may affect responsiveness to the combinatorial treatment of caffeine+AIH.

28. Missing data

Rigorous efforts will be made to ensure complete outcome data. However, we anticipate that participants in this study cohort may be unable to complete the study requirements. Missing data will be reported and documented as we did in our previous clinical trial.⁴⁰ We will document reasons for missing data and our approach to handle missing data during statistical analysis. We will account for potential outliers in our results using a conservative outlier labeling technique set forth by Hoaglin and Tukey.⁴¹

29. Additional analyses

We do not anticipate any additional statistical analyses methods.

30. Harms

Checklists and note pages are used to log any deviations or omissions from the protocols. Any clinical/health related issues would be immediately presented to the subject to determine appropriate notification (i.e., current physician or appropriate specialist). Based on the seriousness of the situation Drs. [name] or [name] may be contacted to provide clinical guidance on the appropriate course of action as per our Laboratory Medical Emergency Safety Plan.

31. Statistical software

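### Protocol 11a excludes randomised people with caffeine side effects without saying from what, and SAP 20 defines no efficacy set that keeps them

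*Combined protocol and SAP*

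**What the plan says.** - Protocol 11a, caffeine intervention: "Persons experiencing caffeine-induced adverse side effects (e.g., dizziness) will be excluded". The sentence does not say from what.
- Protocol 11a, intervention procedures, on design: "Participants will receive three combinatorial interventions in random order: placebo+AIH, caffeine+AIH, caffeine+SHAM". On timing: "Participant enrollment and allocation will be completed during the screening visit".
- Protocol 10, exclusion criterion 9: "Participants with a history of caffeine allergies or intolerances will be excluded from participating in the caffeine study".
- Protocol 11b, repeated in SAP 13: "The interventions will be stopped, and immediate care provided if any significant adverse effects, such as rapid heart rate, dizziness, nausea". Both add that adverse effects are to be reported and assessed. Neither mentions removing a person or their data.
- SAP 20, headed as analysis populations: "We anticipate all participants will participate in the 3 interventions as prescribed". It also expects full attendance and no serious violations. It names no intention-to-treat, full or per-protocol set for efficacy.
- SAP 28: "we anticipate that participants in this study cohort may be unable to complete the study requirements". The way missing data will be handled is left to be documented later.
- SAP 11 and Protocol 14 set N at 20, a figure that "includes 17% attrition rate".
- SAP 26 and 27 analyse the 10MWT at BL, D5, F1 and F2 in a linear mixed model with subject as random effect.

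**The concern.** Leaving out randomised people because of something the study drug did to them is a selection made after randomisation. The contrast of main interest is caffeine+AIH against placebo+AIH, and the people at risk of removal are those who react badly to caffeine. If they drop out of the analysis, the trial answers a question about caffeine tolerators rather than about everyone randomised.

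The plan leaves the choice open. No efficacy set says who counts, and no missing-data method is fixed in advance. SAP 14 keeps allocation concealed only until data collection ends, so the choice could be made with allocation known. In a trial of 20, each person is 5% of the sample. The anticipated difference of 0.06 m/s (SAP 11) equals the clinically important difference in Protocol 12, so there is no margin to absorb even a modest overstatement.

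**Working it through.** **1. Does the rule act after randomisation?** Allocation is completed at screening (Protocol 11a and 13), before the first capsule on treatment day 1. A history of intolerance is already an eligibility criterion, and Table 1 schedules no test dose. The sentence can therefore only add something for people already allocated.

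**2. The same event in four places**

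| Place | What happens to someone with, say, dizziness |
|---|---|
| Protocol 11a | The person is excluded; scope not stated |
| Protocol 11b, SAP 13 | The intervention is stopped; the event is reported |
| SAP 20 | Not foreseen; all are expected to complete |
| SAP 28 | Non-completion expected; handling not fixed |

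The protocol can be explicit when it wants to be: for autonomic dysreflexia, Protocol 18 states that participation ends.

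**3. The plan's own attrition figure.** A critical value of F with 3 and 12 degrees of freedom is 3.49, matching the stated 3.5. Read as a between-group repeated-measures calculation with 4 treatments, 12 + 4 = 16 analysed participants. Then 16 / (1 − 0.17) = 19.3, rounded up to 20, so N is reproduced on that reading. The allowance amounts to 20 × 0.17 = 3.4 people lost, which cannot be squared with the full completion expected in SAP 20. Nothing below depends on this calculation.

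**4. What data would an excluded person have?** Three interventions give 6 possible orders.
- In 4 of 6, a caffeine round comes first. A person excluded in that round has no completed round.
- In 2 of 6, placebo+AIH comes first. Only that round is complete.

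If exclusion falls in the first caffeine round, no order yields a completed caffeine+AIH and placebo+AIH pair. Someone stopped on days 1 to 4 who is not followed has none of that round's analysed post-baseline values (D5, F1, F2).

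**5. Size, as an illustration.** Inputs: an excluded fraction q of 1, 2 or 3 in 20 (assumed, as no rate is given) and an effect in those kept of 0.06 m/s (SAP 11). If the excluded would gain nothing, the all-randomised effect is 0.06 × (1 − q), and the overstatement is 1/(1 − q) − 1. If they would gain half as much, the overstatement is 1/(1 − q/2) − 1.

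| q | All-randomised effect, excluded gain nothing | Overstatement, gain nothing | Overstatement, gain half |
|---|---|---|---|
| 0.05 | 0.057 m/s | 1/0.95 − 1 = 5% | 1/0.975 − 1 = 2.6% |
| 0.10 | 0.054 m/s | 1/0.90 − 1 = 11% | 1/0.95 − 1 = 5.3% |
| 0.15 | 0.051 m/s | 1/0.85 − 1 = 18% | 1/0.925 − 1 = 8.1% |

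If the excluded would gain as much as the others, the overstatement is zero.

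**6. Could it arise at all?** The chance of at least one such person among 20 is 1 − (1 − q)^20: 64%, 88% and 96% for q = 0.05, 0.10 and 0.15.

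**The case against.** The best defence is that the sentence concerns conduct, not analysis. It sits among dosing procedures, and the parallel text in Protocol 11b and SAP 13 only stops the interventions. The mixed model is chosen partly because it copes with incomplete data. SAP 24 measures completeness of follow-up against everyone enrolled and sends reasons for lost data to the CONSORT diagram. This much stands: no text orders the deletion of collected data. A reader might infer that efficacy will be estimated only in tolerators, but the documents show silence, not an instruction to that effect.

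A reader might also infer that caffeine harms vanish from the safety data with the person. The documents contradict this. SAP 20 performs safety assessments on every participant, SAP 19 records adverse events with causality and outcome, and SAP 13 has adverse effects reported. The incidence-rate denominators in Protocol 18 allow for people lost through an adverse event. What remains is smaller: those rates cover only hypertension and autonomic dysreflexia, and no safety set is defined.

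Three further inferences are not supported:
- That exclusion can happen only in caffeine rounds. Staff are blinded and could attribute dizziness to caffeine in a placebo round.
- That calling an effect caffeine-induced reveals the allocation. Two of the three rounds contain caffeine, and a judgement made under blinding is not an unblinding.
- That those who tolerate caffeine are those who respond to it. Nothing in the documents links the two.

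Finally, the number excluded may be small. Known intolerance is screened out, and Protocol 11a cites studies without reported adverse effects at 6 mg/kg. That bears on the size, not on the gap in the plan.

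**Conclusion.** The point holds as a contradiction with a consequence. Protocol 11a removes randomised people because of a study-drug effect, Protocol 11b and SAP 13 describe only stopping treatment, and SAP 20 defines no efficacy set that keeps such people. Applied literally, the rule moves the efficacy estimate toward caffeine tolerators. Whether that happens depends on how the word is applied.

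The 5% to 18% is an illustration. It rests on 1 to 3 exclusions in 20, no benefit in those excluded, and their complete absence from the estimate; it shrinks to zero if they would benefit equally. The statements about incomplete pairs assume exclusion in the first caffeine round. The plan should be changed, but this does not by itself invalidate the trial, and it is not evidence that safety is assessed only in tolerators.

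**What to change.** 1. Reconcile Protocol 11a, Protocol 11b and SAP 13 so that stopping study treatment is distinguished from removing a person's data. The clinical stopping criteria stay as the study physicians set them.
2. In SAP 20, define the primary efficacy set as all randomised participants. Keep every observed round and 10MWT value in the mixed model whatever the reason for stopping. Report participants without post-baseline values by intervention and reason. Do not make a post-baseline 10MWT a condition of entry: that would again drop someone stopped on days 1 to 4 of a first caffeine round and not followed.
3. State that the scheduled D5, F1 and F2 10MWT assessments are still sought after treatment is stopped, where the participant agrees and it is medically acceptable. Without these values the model has nothing to keep for that round and must rely on its missing-data assumption.
4. Summarise adverse events for everyone who took a capsule, by intervention received.
5. Delete the full-completion expectation from SAP 20.

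Items 1, 2, 4 and 5 are wording. Item 3 costs a few visits that are already scheduled, for participants who stop treatment. The other price is a possibly smaller estimated effect.
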